D.1.2. Spinal cord stimulator and stimulation protocol. The 2x2 Soterix® Medical transcutaneous spinal direct current stimulator model 0707-A device will be used. This is a tsDCS available only for investigational use, with which [name] has extensive experience and will provide appropriate training to the study team. This device will be appropriately labeled as an “Investigational Device. Federal (Law) limits device to investigational use”. The device will be kept in a secured area inside the LCOH Research Institute and will be made available only to trained personnel of the study team. This device allows anodal stimulation to be delivered at 2.5mA per 20-minute session or sham session consisting of short pulses (of the desired intensity) at the beginning and end of the sessions. This protocol of anodal stimulation has been reported to be effective in inhibiting ascending pathways with a lasting effect, to be safe and well under the threshold for tissue damage (77, 79). If stimulation intensity (in active or sham protocols) is not tolerable at 2.5mA, the clinician may decide to decrease intensity to 2.0 mA or 1.5 mA. If 1.5 mA stimulation intensity is not tolerated, the subject may be withdrawn from the study. If subject has tolerated a stimulation intensity of less than 2.5mA, the study clinician may attempt to increase the dose to 2.0mA or 2.5mA when considered clinically appropriate. An anode electrode (5x10cm) will be placed at the level of the 10th vertebrae spinal process. At this level, the current is expected to spread longitudinally through the spinal cord up to three additional vertebral levels (96). The cathode (5x7cm) electrode will be placed on the right shoulder over the deltoid area (78, 79, 97). Participants will be scheduled to receive sham or active tsDCS sessions three times/week. Subjects will be randomized in a 1:1 ratio using a simple allocation method to one of two experimental groups: 1) sham or 2) stimulation protocol. Randomization will be double-blinded. An independent operator (trained personnel from the research team) will prepare the tsDCS device parameters for each session, but will not participate in the rest of the assessments. Patients and raters will remain blinded to SCS protocol assigned to each participant throughout the study. During the session, subjects will remain in a calm and relaxing environment. All participants will be scheduled for the same procedures and number of scheduled visits during the eight-week follow-up period. (**Table 2**)

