Primary Outcome: Difference in change from baseline to week 8 (or last available observation) in MADRS scores between active and sham tsDCS groups. **Secondary Outcome:** **a)** differences in AE's frequency between active and sham tsDCS groups, **b)** association between change from baseline to week 8 (or last available observation) in MADRS scores, and clinical (CGI-I, CGI-S, PHQ-9, MAIA, BES and 4DSQ), autonomic (BP, HR) and metabolic (anthropometric, adiponectin, leptin, cortisol, FGF-21 and LCn-3) parameter change from baseline to week 8(or last available observation), and **c)** MADRS sub-component (98) scores, clinical parameters (CGI-I, CGI-S, PHQ-9, MAIA, BES and 4DSQ), autonomic (BP, HR), and metabolic (anthropometric, adiponectin, leptin, cortisol, insulin, FGF-21 and LCn-3) parameters change from baseline to week 8 (or last available observation) difference between Active and Sham tsDCS groups. **Exploratory outcome measures:** **a)** difference in change from baseline to week 8 (or last available observation) in offline ERT and Stop signal task scores between active and sham tsDCS groups; and **b)** difference in change from baseline to week 8 (or last available observation) in offline and online change ERT and stop signal task scores between active and sham tsDCS groups

F. SAFETY MEASURES

Potential Risks. Safety evaluation will consist in recording all laboratory tests, vital signs and ECG results, suicidality monitoring (each SCS session), physical and neurological examinations and any adverse events (AE). As mentioned above, literature suggests that current density below 25 mA/cm² induces no tissue damage (99). Findings will be recorded as AEs at the discretion of the investigator. Known side effects to tsDCS are paresthesia, redness, itch, or pain in stimulated area. If they occur, these side effects tend to disappear within minutes to hours after stimulation. To our knowledge, no serious adverse effects have been reported with the use of transcutaneous direct current stimulation protocols using 2.5mA/cm² (100).

Risk/Benefit Assessment. Participants will be informed that there are other FDA approved treatment alternatives for major depressive disorder and that their participation in this study is voluntary. Therapeutic options include antidepressant medications, psychotherapy, invasive and non-invasive neuromodulation tools. Participants will also be

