Data management and analyses will be organized and performed by the research team under the guidance of [name], Director of the Division of Biostatistics in the Department of Psychiatry at the University of Cincinnati, who has participated in the development of this analytic plan. Data will be collected via Case Report Forms. The research coordinator will be responsible for managing the study flow, maintaining case report forms, and entry data into a password-protected database on REDcap.

Data Analysis. *Specific Aim 1: Prediction 1)* Active tsDCS treatment will result in a greater decrease in depressive symptom severity (MADRS) compared to Sham in adult patients diagnosed with MDD. *Efficacy:* Longitudinal effect of tsDCS will be assessed by comparing change in MADRS scores from baseline to week 8 (or last available observation). To take maximum advantage of intermediate observations while avoiding assumptions about the trajectory of change over time, we will use a repeated-measures ANOVA model (i.e., with time as a categorical variable), and the primary hypothesis test will be a planned contrast of the baseline-week 8 differences between groups. *Prediction 2)* Active tsDCS is safe and well tolerated in adult patients diagnosed with MDD. *Safety:* A similar analysis as used for efficacy data will be performed for laboratory assays, vital signs, anthropometric, clinical, autonomic and metabolic variables. Frequencies of AE's will be compared between groups using comparative analysis. *Specific Aim 2: Prediction 3)* Baseline and change in interoceptive awareness,

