Adverse events will be monitored during the study by the clinical research team, which includes Psychiatrists and a Neurologist and collectively have extensive experience conducting clinical investigation of mood disorders and in the case of [name], the use of transcutaneous spinal direct current stimulation for neurological rehabilitation. They also will be responsible for evaluating and documenting all adverse events during study visits or more frequently as necessary. Additionally, a study-related physician will be accessible by phone to patients 24 hours/day, 7 days/week during study participation. [name] and designated clinical researchers will be responsible for reviewing all laboratory and safety measures from all subjects following each visit. An adverse event (AE) is any unexpected medical occurrence in a patient or clinical investigation subject who is administered a product and which does not necessarily have a causal relationship with the treatment. This includes any clinical or laboratory change that occurs at any time following consent that does not typically occur in that subject and is considered clinically significant. The frequency and severity of all observed or volunteered AEs regardless of treatment group or suspected causal relationship to the study treatment will be recorded throughout the study. [name] and designated clinicians will also be responsible for determining causal relationships between the study treatment and all AEs. Withdrawal from the study as a result of an AE or because of therapeutic measures taken to treat an AE will be at the discretion of the PI. If a subject withdraws or is withdrawn from the study for any reason, a study physician will monitor subjects with any ongoing AE until the AE is resolved or determined to be stable. All AEs (including those present during screening) will be reported. However, for analytics purposes, only post-baseline (randomization) AEs (or AEs that are present at visit 1/ baseline but have increased in severity or frequency post-baseline) will be considered for calculating treatment group differences in AEs. All AEs will be reported to the study DSMB, and the IRB at the time of progress reports.

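### Adverse events are compared between arms by frequency only; recorded severity, withdrawals and intensity reductions for intolerance are left out, which is a weak basis for concluding that tsDCS is well tolerated

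*Combined protocol and SAP*

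**What the plan says.** The AE outcome is secondary outcome (a) in section E, Outcomes: "differences in AE's frequency between active and sham tsDCS groups". Section I, Data Management and Analysis, gives its analysis under Prediction 2 in one sentence: "Frequencies of AE's will be compared between groups using comparative analysis". It does not say whether events or patients are counted, and it names no test. Prediction 2 itself is that active tsDCS is safe and well tolerated.

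Section J, Protection of Human Subjects, collects more than this: "The frequency and severity of all observed or volunteered AEs regardless of treatment group or suspected causal relationship to the study treatment will be recorded". It also foresees withdrawal because of an AE. The one analytic role it gives severity is in deciding which events count: besides post-baseline AEs, the group comparison admits "AEs that are present at visit 1/ baseline but have increased in severity or frequency post-baseline".

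Section D.1.2 describes the active condition as "anodal stimulation to be delivered at 2.5mA per 20-minute session" and the alternative as a "sham session consisting of short pulses (of the desired intensity) at the beginning and end of the sessions". It lets the clinician lower the intensity in either arm if it is not tolerated, and says the patient may be withdrawn if the lowest listed intensity is not tolerated. Section F, Safety Measures, describes the expected reactions: "Known side effects to tsDCS are paresthesia, redness, itch, or pain in stimulated area".

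**The concern.** Tolerability depends on how bad reactions are and what they lead to, as well as on how often something is reported. Here both arms receive some current, the expected reactions are local sensations, and AEs are asked about after every session (section D.2). Mild sensations may therefore be reported in both arms. If they are, a comparison of frequencies has little room to separate the arms, and a difference in severity would not appear in it.

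There is a second route to the same problem. If events are counted, a patient whose intensity was lowered or who was withdrawn may contribute fewer later reports. The less well tolerated arm could then look no worse, or even better, on counts.

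The protocol calls this the first study of tsDCS for depression and intends it to support a larger trial. The tolerability statement carried forward would rest on the least informative of the AE measures available, and any severity table produced later would have been chosen after the data were seen.

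**Working it through.** The plan states no AE rate, severity distribution, margin or power for safety, so there is no figure to reproduce. The check sets what is collected against what is compared, then illustrates the consequence with assumed rates.

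**1. Collected against compared.**

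| Item | Provided for in | Compared by arm? |
|---|---|---|
| AE frequency | Section J | Yes (sections E and I) |
| AE severity | Section J | No; used only to admit worsened baseline AEs |
| Withdrawal because of an AE | Section J | Not listed |
| Intensity reduction or withdrawal for intolerance | Section D.1.2 | Not listed |

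**2. Equal frequency, unequal severity.** Inputs: 10 patients per arm (section G); all AE proportions are assumed.

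- Any AE in 8/10 and 8/10: difference = 80% − 80% = 0. Fisher p = 1.00.
- Same patients, moderate or severe in 4/10 active and 0/10 sham: difference = 40 points. Exact (Clopper-Pearson) 95% intervals are 12% to 74% and 0% to 31%.
- Two-sided Fisher p for x/10 against 0/10 is 2·C(10,x)/C(20,x):
  - x = 3: 2·120/1140 = 0.21
  - x = 4: 2·210/4845 = 0.087
  - x = 5: 2·252/15504 = 0.033

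So the frequency comparison can show nothing at all beside a large severity difference. At this size, though, the severity difference must reach 5/10 against 0/10 before it passes 0.05.

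**3. What the frequency test responds to.** If the true proportion with any AE is equal in both arms, Fisher's test at two-sided 0.05 with 10 per arm rejects in 0.76% of trials when that proportion is 80%, and in 0.11% when it is 90%. These are simply its false-positive rates, and they stay the same however different the severities are.

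**4. What a severity comparison could deliver.** Fisher power for moderate-or-worse rates against an assumed 5% on sham:

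| Active rate | Power |
|---|---|
| 30% | 9% |
| 40% | 24% |
| 50% | 43% |
| 60% | 63% |

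The exact two-sided upper limit for 0/10 is 1 − 0.025^(1/10) = 0.308, so no events in an arm still allows a true rate of 31%. This supports reporting with intervals, and does not support a test.

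**5. Lost reports after withdrawal.** Three sessions a week for 8 weeks is 3 × 8 = 24 AE enquiries per patient. A patient withdrawn after session 6 (assumed) misses 24 − 6 = 18 of them. This can lower an event count. It would not remove a patient who has already reported an AE from a count of patients, so the effect depends on a unit that the plan leaves open.

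**The case against.** The strongest reply is that silence is not exclusion. The analysis sentence speaks of frequencies in the plural without unit, type or grade, and could cover frequencies by severity. Section J refers to group differences in AEs generally and uses severity in its counting rule. This stands in part: the plan does not forbid a severity table. But none is specified, and the outcome as written is frequency.

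Other safety information exists. Section I also compares laboratory, vital-sign, clinical and autonomic variables, and the DSMB reviews tolerability data. That is correct, so frequency is the sole measure only for AEs. None of those variables grades local reactions, and DSMB review is oversight and not a prespecified between-arm result.

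Three stronger readings are tempting, and the documents do not support them.

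- *The sham is designed to equalise sensations, so frequencies will match.* Section D.1.2 says what the sham delivers, not that this is its purpose. Brief pulses may cause fewer reactions than a full session, in which case frequency itself would separate the arms. AEs are elicited by open-ended questions, so near-universal reporting of mild sensations is also an assumption.
- *Serious reactions would be lost among mild ones.* Serious AEs are defined separately, go to the IRB and DSMB within 48 hours, and are reviewed by the DSMB as they occur. The gap concerns non-serious reactions of differing severity.
- *Severity should replace frequency as the main comparison.* In a 20-patient pilot that disclaims conventional significance (section G), nothing in the documents calls for that, and the power figures argue against it.

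**Conclusion.** The point holds as a gap in a secondary safety outcome. The plan records severity and provides for withdrawals and intensity reductions, but compares AEs between arms by frequency only. Similar frequencies could therefore coexist with worse severity on active treatment, and if events are counted, reductions or withdrawals could also lower later counts. Frequency alone is a weak basis for the conclusion in Prediction 2.

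The size cannot be taken from the documents. The 0-point against 40-point contrast shows what is possible under assumed rates and is not a forecast. It needs local sensations to be common in both arms, and it is sharpest if patients with any AE are the unit. No stated power figure or decision rule is affected, and nothing here suggests that active tsDCS is in fact less well tolerated. The change should be made because it is cheap and fixes the tolerability summary before unblinding.

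**What to change.** Keep the frequency comparison and state its unit. In secondary outcome (a) of section E and under Prediction 2 in section I, add a descriptive table by arm giving:

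1. patients by maximum post-baseline AE severity, on a named mild/moderate/severe scale graded by blinded staff;
2. patients withdrawn because of an AE or intolerance;
3. patients with any intensity reduction for intolerance.

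Give each proportion an exact 95% confidence interval, with the risk difference between arms, and say that the table is descriptive and not a powered test. Section G already relies on estimates with confidence intervals, so this fits the plan's approach. Blinded grading is feasible because section D.1.2 keeps raters blinded and keeps the device operator out of the assessments.

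The cost is more than wording. The documents name no severity scale, so one must be chosen and applied consistently to the AEs already being recorded. The result is one more table, with wide intervals at 10 per arm. No change to stimulation or withdrawal rules is implied.

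Suggested text: *In addition to AE frequency, the number of patients per arm will be tabulated by maximum post-baseline AE severity, by withdrawal for an AE or intolerance, and by any intensity reduction for intolerance, with exact 95% confidence intervals and risk differences; no formal hypothesis test is planned for this table.*

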Visit 0 (Screening). Subjects will be informed about study procedures and given a written informed consent to sign voluntarily before any study procedure is initiated (See Informed consent form attached to this protocol). Then, the clinical staff will evaluate the participant in order to obtain a psychiatric and medical history. The MINI will be used to confirm MDD diagnosis, the MADRS to evaluate depressive symptom severity and the CSSRS for suicidality. The clinical research team will perform a full neurological and physical evaluation, ECG, cardiovascular measurements, laboratory tests, urinalysis, urine drug test, and a blood pregnancy test (if applicable). After eligibility is confirmed, a baseline visit will be scheduled.

Visit 1 (Baseline). After verification of eligibility, subjects will be randomized to an “active” or to a “sham” tsDCS protocol. Treatment allocation will remain double-blinded throughout the study to raters and study physicians. A MADRS, CGI-S, CSSRS, PHQ-9, 4DSQ, BES and MAIA will be completed. BMI, waist and abdominal circumference, vital signs, blood sample and ECG will be obtained. A physical and neurological evaluation will be conducted. Participants will complete the ERT and SST prior and during the SCS protocol. Each participant will receive the assigned SCS protocol.

SCS sessions (1-24): Three tsDCS sessions per week will be scheduled. A CSSRS will be completed before each SCS session. Blood pressure and heart rate will be evaluated prior and after each tsDCS session. AE's will be assessed after each session through open-ended questions.

Full visits 2, 3, 4, and 5: A MADRS, CSSRS, CGI-S, CGI-I, PHQ-9, 4DSQ, BES and MAIA scales will be completed.

Anthropometric measures (Visit 3, 4, 5), vital signs, and ECG (Visit 4) will be obtained. A blood sample (visit 4), urine drug test (Visit 4) and pregnancy test will be performed if applicable (visit 4). A physical and neurological evaluation will be

conducted (Visit 3, 4, and 6). Participants will complete the ERT and SST prior and during the SCS protocol (Visit 4). Each participant will receive the respective tsDCS protocol. AE's will be recorded after each tsDCS session.

Full Visit 6 (Final visit): A MADRS, CSSRS, CGI-S, CGI-I, PHQ-9, 4DSQ, BES and MAIA scales will be completed.

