Early withdrawal. A subject may voluntarily decide to end participation at any point during the study. Clinical investigators may decide to end study participation of any subject if it is in the best interest and/or safety of the subject. If at any point during the study a patient has a MADRS suicide item score > one point higher than their visit 1 (baseline) score for any one week, or a score of > 4; or active suicidal behavior on the C-SSRS; or appears to the investigator to pose a risk of self-harm or harm to others, the patient may be withdrawn from the study. Additionally, patients will be withdrawn from the study (and referred for treatment as clinically indicated) if there is a worsening of symptoms at visit 2 or later, as indicated by a CGI-I score of ≥ 6 or more at any time during the study or a minimal worsening of symptoms at visit 3 or later as indicated by a CGI-I score of ≥ 5 at 2 consecutive visits, starting at visit 2; or a 50% increase over baseline in total MADRS rating and a total MADRS > 28, at visit 3 or later. Patients will also be withdrawn from the study at week 3 or later if they demonstrate a ten-point increase from baseline in MADRS score for two successive weeks starting at visit 2. In addition, all patients will be assessed with the C-SSRS on every tsDCS session to elicit risks of potential suicidality. During study participation, a study related clinical investigator will closely monitor all study participants at each study visit for suicidal or homicidal ideation, plan, or intent using clinical interviews as well as the information obtained from rating scales. Transient suicidal ideation will not result in study discontinuation or referral for inpatient care since this may be common for patients with major depressive disorder. In order to maximize subject safety, if a subject exhibits active suicidal or homicidal ideation during study participation that, in the judgment of a clinical study investigator, cannot be managed on an outpatient basis, he/she will be withdrawn from the study and referred for inpatient psychiatric care. Patients with active suicidal behavior may be removed from the study based on C-SSRS criteria, as noted above. All subjects who discontinue study participation prior to visit 6 will be asked to voluntarily undergo endpoint study procedures, if feasible. Additionally, all study participants will be provided with study physician contact information and instructed to contact their study physician 24 hours/day, 7 days/week in between visits should suicidal or homicidal ideation or any other emergency situation occur. If a participant becomes pregnant during the study, participation will be stopped, and the event will be documented as a serious adverse event. The participant will be referred for appropriate medical treatment and follow up with primary care physician and followed by the study team throughout the pregnancy and the outcome documented as required by the IRB and institutional guidelines. We have successfully followed this protocol in our prior

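### The C-SSRS is taken before every session but has no planned comparison by arm; emergent suicidality reaches the safety comparison only if an investigator chooses to record it as an AE.

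*Combined protocol and SAP*

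**What the plan says.** **Collection.** D.2 gives the C-SSRS at screening, at baseline and at the full visits. For the stimulation sessions it adds: "A CSSRS will be completed before each SCS session". Section F (Early withdrawal) gives the purpose: "all patients will be assessed with the C-SSRS on every tsDCS session to elicit risks of potential suicidality". Section F (Potential Risks) counts this as safety evaluation: "Safety evaluation will consist in recording all laboratory tests, vital signs and ECG results, suicidality monitoring (each SCS session), physical and neurological examinations".

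**Outcomes.** The one outcome in Section E devoted to safety is secondary outcome (a): "differences in AE's frequency between active and sham tsDCS groups". Secondary outcome (c) lists "clinical parameters (CGI-I, CGI-S, PHQ-9, MAIA, BES and 4DSQ), autonomic (BP, HR), and metabolic" measures. The C-SSRS is not among them, nor is it in the primary or exploratory outcomes.

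**Analysis.** For Prediction 2, Section I applies the efficacy-type analysis to laboratory, vital-sign, anthropometric, clinical, autonomic and metabolic variables. It also compares AE frequencies between groups by an unspecified method. The C-SSRS is not named.

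**Route into the AE data.** Section F says: "Findings will be recorded as AEs at the discretion of the investigator". Section J describes AEs as including a change "that does not typically occur in that subject and is considered clinically significant". For the comparison by arm it counts AEs that begin after randomisation, or that were present at baseline and have since worsened or become more frequent.

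**The concern.** Prediction 2 is a stated hypothesis: that active stimulation is safe and tolerable in MDD. The protocol describes the trial as the first of this technique in the disorder. Suicidality is the risk it monitors at every session, yet every use it states for the C-SSRS concerns an individual: eligibility, risk monitoring and withdrawal. No step turns the records into a result by arm.

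A reasonable investigator could leave new ideation off the AE log. Section F says "Transient suicidal ideation will not result in study discontinuation" and gives as its reason that such ideation may be common in MDD. AEs are elicited by open-ended questions after a session, whereas the C-SSRS is completed before it, and nothing in the plan links the two. If logging is patchy, an imbalance in transient ideation could exist in the trial's own data and appear in no planned result.

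**Working it through.** The documents give no figure for suicidality, so there is no planned number to reproduce. The check is a comparison of sections, followed by arithmetic on what a table by arm could show.

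**1. Where suicidality can enter a comparison by arm**

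| Route | Source | What it delivers |
|---|---|---|
| C-SSRS as an outcome | Section E | Not listed at any level |
| C-SSRS as a clinical parameter | Section E, secondary (b) and (c); Section I, Prediction 4 | Three lists, each with CGI-I, CGI-S, PHQ-9, MAIA, BES and 4DSQ only |
| C-SSRS in the Prediction 2 analysis | Section I | Not named; the word clinical is left undefined there |
| AE frequency | Sections E, F, I, J | Compared by arm, but recording a finding is discretionary |
| MADRS suicide item | Sections E, F, I | Inside the total and the item-level analysis by treatment |

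**2. Number of records**

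- Sessions: 3 per week x 8 weeks = 24. With screening this makes 25 attendances, matching D.2.
- Pre-session C-SSRS records: 24 x 20 patients = 480 at most.
- The first session takes place at Visit 1, so its record precedes any stimulation. Records that could show emergence: 480 - 20 = 23 x 20 = 460 at most.
- The MADRS is scheduled at five visits after baseline (Visits 2 to 6): 5 x 20 = 100 ratings at most. The planned contrast uses the change from baseline to week 8 or last observation.

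**3. What 10 per arm can show**

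- Two-sided 95% Clopper-Pearson upper limit for 0/10: 1 - 0.025^(1/10) = 0.308.
- Fisher's exact test, two-sided, k of 10 v 0 of 10: p = 2 x C(10,k)/C(20,k).
  - k = 4: 2 x 210/4845 = 0.087.
  - k = 5: 2 x 252/15504 = 0.033.
- Against an arm with no cases, at least 5 of 10 are therefore needed to reach two-sided 0.05.
- Exact Fisher power at 10 per arm, under assumed rates (the documents give none):

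| Assumed rates | Power |
|---|---|
| 20% v 10% | 1% |
| 30% v 10% | 6% |
| 40% v 10% | 15% |
| 50% v 10% | 29% |

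The useful product is therefore a count with an interval, not a significance test.

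**The case against.** The strongest reply is that suicidality is already analysed. The MADRS has a suicide item, which Section F uses as a withdrawal trigger. The MADRS total is the primary outcome, and Section I plans an item-level analysis by treatment. This stands, so a reader who infers that suicidality enters no outcome or analysis goes too far. These are, however, depression-severity analyses of change to an endpoint. They do not count patients with emergent ideation and do not capture C-SSRS behaviour.

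Second, the AE route is wider than it may seem. Section J records observed and volunteered AEs whatever their suspected cause and counts worsening from baseline. Its wording about changes atypical for the subject illustrates the AE definition rather than limiting it. The sentence on transient ideation concerns discontinuation and referral, not AE recording. Suicidal behaviour leading to hospitalisation would meet the SAE definition. All this stands. The discretion in Section F remains, and it matters most for ideation managed without admission.

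Third, clinical in the Prediction 2 analysis might be meant to include the C-SSRS. The text does not prove exclusion: Section I groups its variables differently from Section E. It is ambiguous. Even on the generous reading, the analysis would be a repeated-measures ANOVA of change, not a count of emergent cases.

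Fourth, the DSMB reviews safety, tolerability and efficacy data at least every six months, with information on group assignment, and reviews SAEs as they occur. That is real group-level oversight. It does not name the C-SSRS and does not put a comparison by arm into the trial's results.

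Finally, this is a pilot of 20 patients that excludes significant suicide risk. That limits what a table can show but is no reason to omit one.

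**Conclusion.** The point holds as a reporting gap that should be closed. The C-SSRS is a named part of the safety evaluation with no planned summary by arm, and the only defined route for emergent suicidality into the safety comparison is a discretionary AE entry. The stated rules can therefore support a favourable conclusion on Prediction 2 while an imbalance in transient ideation goes unseen.

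Two stronger inferences are not supported. The 480 pre-session records are not unused: they serve individual management, and at most 460 of them could show emergence. Nor would a comparison settle safety, since no cases in 10 patients still allows a true rate of up to about 31%.

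The conclusion rests on the text of Sections D.2, E, F, I and J. Table 2 is not readable in the text available and was not used as evidence of an omission. The record counts assume 20 patients attending every session. The power figures rest on assumed rates.

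**What to change.** Add to secondary outcome (a) in Section E, and to the Prediction 2 analysis in Section I, a descriptive C-SSRS table by arm showing:

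- the number of patients with treatment-emergent suicidal ideation, defined as any C-SSRS category after the first stimulation session (active or sham) higher than the pre-treatment category;
- the number with any suicidal behaviour after randomisation;
- each patient's maximum category after baseline.

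State the recall period for the pre-treatment category as current or recent, not lifetime or past year. Eligibility requires screening for suicidal behaviour over the past year, and a historical event used as the benchmark could mask later emergence.

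Give exact 95% confidence intervals for the proportion in each arm and for the risk difference, and state that safety will not be inferred from a non-significant test. Similar tables for new ECG and neurological-examination abnormalities are optional and not needed for this point.

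The cost is a few sentences of outcome and analysis text and one table from data already scheduled. There is no new assessment, no extra patient burden, and no change to clinical management or sample size.
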